10.6 Reporting of Serious Adverse Events

Any AE that meets any criterion for an SAE requires the completion of an SAE Report Form in addition to being recorded on the AE page/screen of the eCRF. All SAEs must be reported to Celgene Drug Safety within 24 hours of the investigator's knowledge of the event by facsimile, or other appropriate method (eg, via email), using the SAE Report Form, or approved equivalent form. This instruction pertains to initial SAE reports as well as any follow-up reports.

The investigator is required to ensure that the data on these forms is accurate and consistent. This requirement applies to all SAEs (regardless of relationship to IP) that occur during the study (from the time the subject signs informed consent until 42 days after the last dose of IP) or any SAE

made known to the investigator at any time thereafter that are suspected of being related to IP. Serious adverse events occurring prior to treatment (after signing the ICF) will be captured.

The SAE report should provide a detailed description of the SAE and include a concise summary of hospital records and other relevant documents. If a subject died and an autopsy has been performed, copies of the autopsy report and death certificate are to be sent to Celgene Drug Safety as soon as these become available. Any follow-up data should be detailed in a subsequent SAE Report Form, or approved equivalent form, and sent to Celgene Drug Safety.

Where required by local legislation, the investigator is responsible for informing the Institutional Review Board/Ethics Committee (IRB/EC) of the SAE and providing them with all relevant initial and follow-up information about the event. The investigator must keep copies of all SAE information on file including correspondence with Celgene and the IRB/EC.

10.6.1 Safety Queries

Queries pertaining to SAEs will be communicated from Celgene Drug Safety to the site via facsimile or electronic mail. The response time is expected to be no more than five (5) business days. Urgent queries (eg, missing causality assessment) may be handled by phone.

10.7 Expedited Reporting of Adverse Events

For the purpose of regulatory reporting, Celgene Drug Safety will determine the expectedness of events suspected of being related to luspatercept based on the Investigator's Brochure.

In the United States, expedited reports sent to the Food and Drug Administration (FDA) by the sponsor based on the reasonable possibility threshold are known as 'Investigational New Drug (IND) safety reports' and will be reported in accordance with 21 CFR 312.32.

For reporting to the FDA, events that are not suspected to be causally related to luspatercept by the sponsor will not be considered adverse reactions. As per FDA regulations, events that are anticipated in the study population, as detailed in the IB, will not be considered adverse reactions on individual assessment and will be reviewed on an aggregate basis for assessment of frequency.

For countries within the European Economic Area (EEA), Celgene or its authorized representative will report in an expedited manner to Regulatory Authorities and Ethics Committees concerned, suspected unexpected serious adverse reactions (SUSARs) in accordance with Directive 2001/20/EC and the Detailed Guidance on collection, verification and presentation of adverse reaction reports arising from clinical trials on investigational products for human use (ENTR/CT3) and also in accordance with country-specific requirements.

For the purpose of regulatory reporting in the EEA, Celgene Drug Safety will determine the expectedness of events suspected of being related to the other IP, epoetin alfa, based on the UK Summary of Product Characteristics (SmPC).

In addition, if requested, any report of progression to high risk MDS or AML in both the luspatercept and epoetin alfa arm, regardless of causality, will be reported as an expedited safety report to individual health authorities.

Celgene or its authorized representative shall notify the investigator of the following information (In Japan, Celgene KK shall notify the heads of the institutes in addition to the investigators):

- Any AE suspected of being related to the use of IP in this study or in other studies that is both serious and unexpected (ie, SUSAR);
- Any finding from tests in laboratory animals that suggests a significant risk for human subjects including reports of mutagenicity, teratogenicity, or carcinogenicity.
- Other important safety information and periodic reports according to the local regulations.

Where required by local legislation, the investigator shall notify his/her IRB/EC promptly of these new serious and unexpected AE(s) or significant risks to subjects.

The investigator must keep copies of all pertinent safety information on file including correspondence with Celgene and the IRB/EC. (See [Section 14.3](#) for record retention information).

Celgene Drug Safety Contact Information:

For Celgene Drug Safety contact information, please refer to the Serious Adverse Event Report Form Completion Guidelines or to the Pregnancy Report Form Completion Guidelines.

10.8 COVID-19 Reporting

The occurrence of a COVID-19 event will be monitored as part of the assessment of AEs throughout the course of the study. Investigators are to report the occurrence of COVID-19 events, regardless of casual relationship to IP, occurring at any time for the duration of treatment up to 42 days after the last dose.

11 DISCONTINUATIONS

11.1 Treatment Discontinuation

The following events are considered sufficient reasons for discontinuing a subject from the investigational product(s):

- Lack of Efficacy
- Adverse Event
- Withdrawal by subject
- Death
- Lost to follow-up
- Pregnancy
- Protocol violation
- Study terminated by the sponsor
- Other (to be specified on the eCRF)
 - Including treatment discontinuation guidance related to dose modification [Section 7.2.1.2](#) and [Section 7.2.2.2](#) for luspatercept and epoetin alfa, respectively.
- Disease Progression as per IWG criteria for altering natural history of MDS ([Cheson, 2006](#)) ([APPENDIX D](#))
 - For subjects with 5-10% blasts, a second bone marrow sample should be collected within 4 weeks for clinical assessment (eg, cytomorphology, cytogenetics) to confirm progression before discontinuing subjects from treatment.

The reason for discontinuation of treatment should be recorded in the eCRF and in the source documents.

The decision to discontinue a subject from treatment remains the responsibility of the treating physician, which will not be delayed or refused by the sponsor. However, prior to discontinuing a subject, the investigator may contact the Medical Monitor and forward appropriate supporting documents for review and discussion.

An EOT evaluation will be performed for all subjects who are withdrawn from treatment with IP for any reason as soon as possible after the decision to permanently discontinue treatment has been made ([Section 6.2.2](#)). Subjects who received at least one dose of IP will enter the Post-treatment Follow-up Period ([Section 6.3](#)).

11.2 Study Discontinuation

The following events are considered sufficient reasons for discontinuing a subject from the study:

- Screen failure
- Withdrawal by subject
- Death
- Lost to follow-up
- Protocol violation

- Study terminated by sponsor
- Other (to be specified on the eCRF)

The reason for study discontinuation should be recorded in the End of Study eCRF and in the source documents.

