6.1.19 Monitoring for Progression to AML and Other Malignancies/Pre-malignancies

Progression to AML as per WHO classification ([Arber, 2016](#)) will be monitored and will be included as part of the safety assessment throughout the course of the study. Progression to AML should be monitored from time of signing of informed consent through 5 years after the first dose of IP, or 3 years from the last dose (whichever occurs later), or until death, lost to follow-up or withdrawal of consent from the study. For that purpose, subjects will be followed post treatment every 12 weeks for 3 years from the date of last dose of IP and every 6 months thereafter, if applicable.

The occurrence of a new malignancy or pre-malignant lesion will be monitored as an event of interest and should be included as part of the assessment of AEs throughout the course of the study (please refer to [Section 10.5](#) for details). Investigators are to report the development of any new

malignancy or pre-malignant lesion as a serious adverse event (SAE), regardless of causal relationship to IP (luspatercept or epoetin alfa), occurring at any time for the duration of the study, from the time of signing the ICF for up to and including long-term follow-up (ie, 5 years from first dose of IP, or 3 years from last dose [whichever occurs later]), or until death, lost to follow-up, or withdrawal of consent for further data collection.

Documentation supporting the diagnosis of progression to AML and other malignancies/pre-malignancies (eg, confirmatory histology or cytology results, etc.) may be requested. Appropriate information related diagnosis of AML and other malignancies/pre-malignancies should be captured on the eCRF and in the subject's source documents.

Refer to [Section 10.5](#) and [Section 10.6](#) for more information regarding reporting requirements.

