6.3.2 Long-term Follow-up

Transfusion data collection will continue until 8 weeks from the date of last dose of IP or from the date of the EOT Visit (whichever is later) ([Section 6.4.1](#)). Subjects should also be followed via telephone contact by the site to verify if transfusions were given outside of the investigative site.

Antidrug antibodies sample(s) may be required in the Post-treatment Follow-up Period for subjects assigned to the luspatercept arm, who terminate the Treatment Period with less than 1 year of ADA monitoring if a subject is ADA positive at the time of treatment discontinuation ([Section 6.6](#)).

An additional pregnancy test is to be performed 12 weeks (± 7 days) from the date of last dose of IP for FCBP ([Section 6.1.14](#)).

All subjects discontinued from protocol-prescribed therapy for any reason should be followed for the below events/therapies for 5 years after the first dose of IP, or 3 years from the last dose (whichever occurs later), or until death, lost to follow-up or withdrawal of consent from the study.

- Progression to AML and other malignancies/pre-malignancies (please refer to [Section 6.1.19](#) and [Section 10.5](#) for details)
- Survival (date and cause of death)
- and subsequent MDS therapies

Subjects may be followed via telephone contact by the site for collection of the above data every 12 weeks for the first 3 years from the date of last dose of IP and every 6 months thereafter (if applicable) until 5 years after the first dose of IP, or 3 years from the last dose (whichever occurs later), or until death, lost to follow-up or withdrawal of consent from the study. Refer to [Table 3](#).

Data regarding subsequent MDS therapies, determination of AML progression and other malignancies/pre-malignancies, and date and cause of death will be recorded in the eCRF. The investigator must make every effort to obtain information regarding the subject's survival status before determining the subject is lost to follow-up. If the subject is discontinued from Long-term Follow-up, the reason for discontinuation should be recorded on the End of Study eCRF.

Long-term follow-up may be conducted by record review (including public records if allowed by local regulations) and/or telephone contact with the subject, family, or the subject's treating physician.

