8 CONCOMITANT MEDICATIONS AND PROCEDURES

Over the course of this study, additional medications may be required to manage aspects of the disease state of the subjects, including side effects from trial treatments or disease progression. Supportive care may be administered at the discretion of the investigator.

All prior/ concomitant medications, used 8 weeks prior to randomization until 42 days after the last dose of IP, must be reported on the eCRF. All prior procedures within the 8 weeks prior to randomization as well as concomitant procedures will be recorded on the appropriate eCRF. All transfusions will be reported on the eCRF for at least 16 weeks prior to randomization until 8 weeks after last dose of IP or the EOT Visit, whichever occurs later.

Prior anticancer treatments should be recorded on the appropriate eCRF(s) regardless of treatment discontinuation/procedure date.

Prior iron chelation therapy should be recorded on the appropriate eCRF(s) regardless of treatment discontinuation date.

If a subject requires treatment with any new medications that are specifically excluded in [Section 8.2](#), the subject will be discontinued from treatment and should complete the EOT visit and enter the Post-treatment Follow-up Period of the study. The investigator should consult the medical monitor regarding any questions about whether a new medication or dosage of existing medication would require the subject to discontinue from the study.

For information regarding other drugs that may interact with IP and affect its metabolism, pharmacokinetics, or excretion, please see the Investigator's Brochure and/or local package insert.

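### Section 11.2 allows study exit for protocol violation or an open Other category, which the AML, malignancy and survival follow-up rules do not provide for

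*Combined protocol and SAP*

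**What the plan says.** Section 11.2 lists seven events under the lead-in "The following events are considered sufficient reasons for discontinuing a subject from the study". Two of them are "Protocol violation", with no qualifier, and an open Other to be specified on the case report form. The section ends: "The reason for study discontinuation should be recorded in the End of Study eCRF and in the source documents".

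Section 6.3.2 reads differently: "All subjects discontinued from protocol-prescribed therapy for any reason should be followed for the below events/therapies". The items are AML and other malignancies or pre-malignancies, survival, and subsequent MDS therapies. The planned end is the later of 5 years after first dose and 3 years after last dose. The early exits, in 6.3.2 and for AML in 6.1.19, are given as "or until death, lost to follow-up or withdrawal of consent from the study". The Protocol Summary, 3.1, 3.2 and the malignancy row of Table 3 name the same three.

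Section 8 says that a subject who needs a newly started excluded drug stops treatment, has the EOT visit and enters Post-treatment Follow-up. The next sentence asks the investigator to consult the medical monitor about "whether a new medication or dosage of existing medication would require the subject to discontinue from the study".

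Section 11.1 lists protocol violation and Other as reasons for stopping treatment, and sends every subject with at least one dose into Post-treatment Follow-up.

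**The concern.** The protocol separates stopping treatment (11.1) from leaving the study (11.2), and the long-term endpoints depend on that separation. If a dosed subject can leave the study for a protocol violation or an unspecified other reason, follow-up can end while the subject is alive, reachable and still consenting.

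Two things are at stake. First, time to AML and overall survival are secondary endpoints. Section 9.7.2 censors at the last assessment without AML and at the date last known alive. An early close-out therefore becomes a censored observation. If the reason for it is related to how the subject is doing, the censoring is informative; with treatment known to all, it may also differ by arm. Second, 1.4.1.1.1 names long-term follow-up under 6.3.2 as a safeguard for the hematologic-malignancy risk seen in juvenile rats. A subject closed out early is no longer under that scheduled monitoring.

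**Working it through.** The plan states no figure on this point, so the main check compares the lists.

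**Step 1. Match the seven reasons in 11.2 to the early exits in 6.3.2.**
- Withdrawal by subject, death, lost to follow-up: all three match.
- Screen failure: arises before randomization, so no counterpart is needed.
- Study terminated by sponsor: a trial-level decision covered in 3.3 and 13.8.
- Protocol violation: no counterpart.
- Other: no counterpart.

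Count: 7 − 3 − 1 − 1 = 2 reasons without support in any follow-up rule.

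**Step 2. Does a benign reading remove the conflict?**
- Treatment only: no. Section 11.1 already carries both reasons for treatment, and 11.2 is a separate list for the study.
- Before randomization only: no. Screen failure is its own item, and protocol violation carries no limit.
- Follow-up continues anyway: nothing says so. Section 11.2 uses the End of Study form, 6.3.2 uses that form for leaving Long-term Follow-up, and End of Study is the last column of Table 3, referenced to 11.2.

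**Step 3. What is still captured after close-out?** Under 10.1, from 42 days after the last dose, only serious events that the investigator learns of and suspects are drug-related. Section 6.1.19 asks for new malignancies regardless of causality, which is broader and depends on continued contact.

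**Step 4. Can the effect be sized?** Not from the documents. As an illustration, assume 2% to 5% of 350 subjects are closed out this way: 0.02 × 350 = 7 and 0.05 × 350 = 17.5. Appendix C gives the time to 25% AML as 10.8 years (low risk) and 3.2 years (intermediate risk). With a constant hazard:
- Low: −ln(0.75)/10.8 = 0.0266 per year, and 1 − exp(−5 × 0.0266) = 12.5% at 5 years.
- Intermediate: −ln(0.75)/3.2 = 0.0899 per year, and 1 − exp(−5 × 0.0899) = 36.2% at 5 years.

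If all 350 subjects had the low or the intermediate risk, there would be about 44 (350 × 0.125) or 127 (350 × 0.362) AML events. Events among those closed out would number about 7 × 0.125 = 0.9 to 17.5 × 0.362 = 6.3. If their risk is average, the missed share is at most the removal rate itself, because (r × 350 × p)/(350 × p) = r for any risk p. A larger share needs removed subjects to be at higher risk than the rest, and the documents give no figure for that. These risks also ignore competing death (median survival for intermediate risk is 3.0 years in Appendix C) and the trial's restriction to marrow blasts below 5%.

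**The case against.** The strongest reply is that 11.2 is a generic disposition list. It names no decision-maker, orders no removal and does not say that AML or survival follow-up ends. All of that is correct: that follow-up ends is an inference from leaving the study, the End of Study form and Table 3. The inference stands because nothing in the protocol points the other way for these two reasons.

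A reader might infer that the usual case is a subject with failing response who starts lenalidomide, a hypomethylating agent or an outside ESA and is then dropped. The documents do not support that. Section 8 sends a subject who needs an excluded drug into follow-up, 11.1 does the same for every dosed subject who stops treatment, and 6.3.2 collects subsequent MDS therapies as expected data. The later phrase in Section 8 blurs this rule but does not replace it.

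It is also fair that the two categories have a legitimate use. Section 6.2.2 foresees randomized subjects who were never dosed, and 11.1 routes only dosed subjects into follow-up. An undosed subject found ineligible needs some entry on the End of Study form, so deleting the category for everyone would go too far.

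Finally, AML progression and overall survival lie outside the gate-keeping order in 9.7.2, so no confirmatory claim rests on them. That limits the consequence, but the safety purpose of the follow-up remains.

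**Conclusion.** The inconsistency is real and should be corrected. Section 11.2 permits study exit for two reasons that no follow-up rule recognises, and Section 8 leaves a similar doubt. For a dosed subject, the literal result is avoidable censoring of time to AML and overall survival, possibly informative, and loss of scheduled malignancy monitoring.

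The size is unknown. The documents give neither the number of such exits nor the risk of the subjects concerned, and the direction of any bias cannot be stated. A reader might infer that a visible share of AML events would be lost; that needs both an assumed removal rate and an assumed concentration of high-risk subjects among those removed, and neither is in the documents. The primary endpoint, a response rate over Weeks 1 to 24 in the ITT population, and the 90% power with 350 subjects do not depend on this point.

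The conclusion rests on one assumption: that discontinuing from the study means the end of scheduled data collection.

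**What to change.** In 11.2, remove protocol violation as a study-discontinuation reason for subjects who received at least one dose, and limit Other to reasons that make further data collection impossible. Keep a disposition category for randomized subjects who were never dosed. Section 11.2 would then agree with 6.3.2 and the other follow-up rules.

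In Section 8, reconcile the phrase about leaving the study with the sentence before it, which keeps the subject in follow-up.

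These changes concern data collection only. The treatment-discontinuation reasons in 11.1 stay as they are.

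The cost is two wording changes, one eCRF pick-list change and a few more follow-up contacts, by telephone or record review as 6.3.2 already allows. Data not collected after an early close-out may not be recoverable, so the change is worth making before such exits occur.

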12 EMERGENCY PROCEDURES

12.1 Emergency Contact

In emergency situations, the investigator should contact the responsible Clinical Research Physician/Medical Monitor or designee by telephone at the number(s) listed on the Emergency Contact Information page of the protocol (after title page).

In the unlikely event that the Clinical Research Physician/Medical Monitor or designee cannot be reached, please contact the global Emergency Call Center by telephone at the number listed on the Emergency Contact Information page of the protocol (after title page). This global Emergency Call Center is available 24 hours a day and 7 days a week. The representatives are responsible for obtaining your call-back information and contacting the on-call Celgene/contract research organization Medical Monitor, who will then contact you promptly.

Note: The back-up 24-hour global emergency contact call center should only be used if you are not able to reach the Clinical Research Physician(s) or Medical Monitor or designee for emergency calls.

12.2 Emergency Identification of Investigational Products

This is an open-label study; therefore, IP will be identified on the package labeling.

13 REGULATORY CONSIDERATIONS

13.1 Good Clinical Practice

The procedures set out in this study protocol pertaining to the conduct, evaluation, and documentation of this study are designed to ensure that Celgene, its authorized representative, and investigator abide by Good Clinical Practice (GCP), as described in International Council for Harmonisation (ICH) Guideline E6 and in accordance with the general ethical principles outlined in the Declaration of Helsinki. The study will receive approval from an IRB/EC prior to commencement. The investigator will conduct all aspects of this study in accordance with applicable national, state, and local laws of the pertinent regulatory authorities.

13.2 Investigator Responsibilities

Investigator responsibilities are set out in the ICH Guideline for Good Clinical Practice and in the local regulations. Celgene staff or an authorized representative will evaluate and approve all investigators who in turn will select their staff.

The investigator should ensure that all persons assisting with the study are adequately informed about the protocol, amendments, study treatments, as well as study-related duties and functions, including obligations of confidentiality of Celgene information. The investigator should maintain a list of Sub-investigators and other appropriately qualified persons to whom he or she has delegated significant study-related duties.

The investigator is responsible for keeping a record of all subjects who sign an informed consent form (ICF) and are screened for entry into the study. Subjects who fail screening must have the reason(s) recorded in the subject's source documents.

The investigator, or a designated member of the investigator's staff, must be available during monitoring visits to review data, resolve queries and allow direct access to subject records (eg, medical records, office charts, hospital charts, and study-related charts) for source data verification. The investigator must ensure timely and accurate completion of eCRFs and queries.

The information contained in the protocol and amendments (with the exception of the information provided by Celgene on public registry websites) is considered Celgene confidential information. Only information that is previously disclosed by Celgene on a public registry website may be freely disclosed by the investigator or its institution, or as outlined in the Clinical Trial Agreement. Celgene protocol, amendment and IB information is not to be made publicly available (for example on the investigator's or their institution's website) without express written approval from Celgene. Information proposed for posting on the investigator's or their institution's website must be submitted to Celgene for review and approval, providing at least five (5) business days for review.

At the time results of this study are made available to the public, Celgene will provide investigators with a summary of the results that is written for the lay person. The investigator is responsible for sharing these results with the subject and/or their caregiver as agreed by the subject.

